	
One main part of the procedure to repair a hernia involves the placement of a prosthetic (a device that substitutes for missing parts or pieces) mesh to reinforce the abdominal wall and allow for a tension free repair. The use of the mesh also helps to lower the recurrence rate (the chance that the hernia will come back). The most common type of mesh prosthesis that is placed in laparoscopic inguinal hernias is a polypropylene (the substance the mesh is composed of) mesh which has been shown to be safe and effective.
 
There is some emerging evidence that a "lighter weight" form of this mesh may improve quality of life outcomes following surgery and is the mesh currently being used at New Hanover Regional Medical Center for laparoscopic inguinal hernia repair. However, there are many different "light weight" polypropylene meshes on the market that are FDA approved and available for use. Currently, there are two different forms of the mesh being used interchangeably for the procedure at NHRMC. Both of these meshes have had good clinical outcomes.
 
The purpose of this research study is to evaluate the clinical effectiveness of the two meshes currently being used. The study may provide evidence on whether one mesh is more effective than the other. A secondary goal of the study is to evaluate the ease of use and time it takes residents to place and perform the surgery using these two different meshes. This information may make it possible to determine if one mesh is easier for residents to use during surgery and therefore take them less time to perform the procedure.
 
The effectiveness of the meshes will be measured by the patient's length of hospital stay, perioperative complications, recurrence rate, patient pain score and/or comfort level and the patient's postoperative quality of life.

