
2. Description of study design, methods, and procedures, describe the study in sequential order as it is to be conducted at this institution. The following should be included:
 
 ➤ type of experimental design ➤ study procedures: a sequential description of what will be asked of/done to subjects (to include identification and recruitment of subjects, consent process, treatment or intervention if applicable, length of participation, additional visits, follow-up, etc.) ➤ description and assignments of subjects to various arms of the study (if applicable) 	
This will be a prospective open-label randomized study conducted by [name] from the study's approval date to until December 31, 2015. Approximately five-hundred (500) subjects will be enrolled in this study.
 
Patients presented to NHRMC, the Outpatient Surgery Clinic, SEAHEC Physicians' Office, Inpatient Surgical Units at NHRMC and/or the Emergency Department for abdominal wall hernia repair during their pre-operative visit and who meet the inclusion and exclusion criteria will be counseled by [name] on surgical options for repair to determine if they would

- doses, frequency, and route of administration of medication and other treatment
- data that will be collected
- primary outcome measurements
- follow-up procedures
- If the study involves clinical activities, distinguish routine care procedures from those that are study specific

rather undergo an open or laparoscopic repair. If the patient is a candidate and agrees with undergoing the laparoscopic repair, they will be asked if they would like to participate in a randomized trial comparing two different meshes. If the patient agrees, he/she will be presented with information regarding this study. The study will then be explained to the patient by [name].

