[name] will give the patients the informed consent document at New Hanover Regional Medical Center, Outpatient Surgery Clinic, SEAHEC Physicians' Office, Inpatient Surgical Units at NHRMC and/or the Emergency Department. [name] will review the page-by-page informed consent document with the patients. A copy of the informed consent document explaining the objectives and associated risks and benefits of the study will be given to the patient. The patient will be allowed to read and review the elements of the informed consent document. Patients will have a chance to ask [name] any questions they may have about the surgery and the study. If necessary, the patient will be allowed additional time to review the document. After receiving verbal consent, [name] will obtain written consent from the patient. A copy of the signed informed consent document will be given to the patient and another copy will be placed into the patient's medical record. The original document will be placed into a separate secure file cabinet that will be locked at all times.

On the day of surgery, patients agreeing to participate in the study will be randomized to receive either one of two meshes - ultrapro mesh (Ethicon) or bard 3d max (Bard). This randomization will occur with a random pattern being generated using an electronic random number generator. Then, the random assignments will be placed inside opaque, sequential envelopes. The envelopes will be opened, in order, which will guarantee a random assignment of subjects to each study arm.

Prior to the surgery, patients will be given the Carolinas Comfort Scale (CCS) and Visual Analog Scale (VAS). These study specific scales will be used to access the patients' pain and/or comfort level prior to surgery and should take no longer than 5 minutes to complete. The CCS uses a patient questionnaire of 8 questions to establish a quality measure for pain. Patients are asked to rate, on a scale of 0 to 5, sensation of mesh, pain and movement limitations during the following activities: lying down, sitting up, activities of daily living, coughing or deep breathing, walking or standing, walking up or down stairs, and while performing non-work related exercising. The VAS

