helps patients to say how good or bad their health state is. This scale uses a line with two different extremes. The extremes can vary in forms. Some VAS can ask the patient to range their pain level or current health status on a rating of either 0-10 (with 0 being no pain and 10 being the worst possible pain) or by choosing a picture of a happy or sad face.

Patients with bilateral inguinal hernias (an abnormal opening or defect that occurs on both sides of the groin), either found preoperatively or intra-operatively, will be treated as one hernia and will have the same mesh placed on both sides. Cases will be performed by one attending using his standard technique for laparoscopic inguinal hernia repair.

Data to be collected will include the patients' demographic information (age, sex, race), comorbidities (if present), smoking history, drinking history, medications, allergies and previous surgeries.

Operative data will include the following: type of anesthesia (all patients will undergo general), technique of laparoscopic access, type and side of hernia (direct or indirect), size of mesh used, type and number of tacks used to secure mesh, operative time, blood loss, urine output, and type and technique of closure.

Postoperative data will include: length of hospital stay, perioperative complications, recurrence rate, patient pain score and patient's postoperative quality of life. Further follow up data will include an assessment of the patient's recurrence rate, pain scale and quality of life during the patient's 1-2 weeks, 6 months, and 1 year follow-up. The patient will also be asked to rate their pain and/or comfort level by using the CCS and/or the VAS. During their 1-2 weeks visit, the patient will be informed of the 6 and 1 year follow-ups. For the six (6) month and one (1) year follow-up the patient will be contacted by telephone and/or be asked to return to the SEAHEC Physician's Office. The patient will not be charged for any of these services. Subjects will be tracked and identified with the use of the research record that will be set up in EPIC. Patients will be associated with the study and their surgery admission will be associated with the study for billing and coding compliance. In case the above system does not work, as a secondary system, patients will be tracked using an excel spreadsheet.

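### The trial is open-label with no stated reason although pain and comfort are patient-rated; not telling patients their mesh would cheaply reduce, not remove, reporting bias

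*Combined protocol and SAP*

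**What the plan says.** Part IV, item 2 (study design, methods and procedures) begins: "This will be a prospective open-label randomized study conducted by" the investigator. The text reviewed gives no reason for this and does not say that the patient, the person collecting follow-up or the statistician is masked.

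Part IV, item 1 lists the effectiveness measures as "length of hospital stay, perioperative complications, recurrence rate, patient pain score and/or comfort level" and postoperative quality of life. No single primary outcome is named. Item 2 then describes how these are measured and compared:

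- The CCS is a patient questionnaire scored 0 to 5 on "sensation of mesh, pain and movement limitations during the following activities". The VAS is described as something that "helps patients to say how good or bad their health state is". CCS and/or VAS are given before surgery and used again in follow-up at 1-2 weeks, 6 months and 1 year.
- Candidates are asked whether "they would like to participate in a randomized trial comparing two different meshes", so they know what is being compared.
- Assignment follows consent: "On the day of surgery, patients agreeing to participate in the study will be randomized to receive either one of two meshes". It uses opaque envelopes opened in order.
- All patients have general anesthesia, and one attending uses his standard technique.
- Outcomes are compared by resident level and mesh type, with p<0.05 as the criterion.

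Item 1 also says that the two meshes are used interchangeably at the hospital, and adds: "Both of these meshes have had good clinical outcomes".

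**The concern.** A patient who knows which mesh was implanted may answer questions about pain, and especially about feeling the mesh, in light of that knowledge. A change common to both arms cancels in the comparison. A change that differs between arms does not: it adds directly to the observed difference. More patients will not remove it, and the planned comparison has no means of separating it from a true mesh effect. Opaque envelopes hide the next assignment from whoever enrolls the patient; they do nothing once the envelope is open.

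Quality of life is probably exposed in the same way, since no separate instrument is named and the VAS is described in terms of health state. Recurrence may also rest partly on the patient's report when the 6-month or 1-year contact is by telephone; the text does not say.

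A smaller related gap is that item 2 does not say whether the preoperative CCS and VAS are completed before the assignment is known.

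**Working it through.** **Is masking the patient practicable?** Set side by side, the statements in Part IV suggest that it is. Assignment comes after consent on the day of surgery, anesthesia is general for everyone, the same attending uses his standard technique, and both devices are already in routine use. The patient therefore has no evident need to be told the mesh in order for the operation to proceed.

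**How large could the effect be?** The plan has no figure to reproduce on this point: it states no effect size, SD, power or test. What follows is an illustration only.

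Inputs from the plan:
- about 500 patients (Part IV, item 2);
- significance at p<0.05 (Part IV, item 2).

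Assumptions:
- equal arms, so n = 250 each;
- a two-sided z test comparing means;
- no true mesh difference;
- complete follow-up;
- a between-arm reporting shift of d SD among patients who know their mesh;
- a share f of each arm that knows it, so that the expected shift is f × d.

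Smallest observed difference declared significant: 1.96 × √(2/250) = 0.175 SD.

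P(false p<0.05) = [1 − Φ(1.96 − fd√(n/2))] + Φ(−1.96 − fd√(n/2)), with √(250/2) = 11.18.

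- d = 0, any f: 0.025 + 0.025 = 0.050.
- d = 0.05, f = 1: 0.05 × 11.18 = 0.559, giving [1 − Φ(1.401)] + Φ(−2.519) = 0.0806 + 0.0059 = 0.0865.
- d = 0.10, f = 1: 0.10 × 11.18 = 1.118, giving [1 − Φ(0.842)] + Φ(−3.078) = 0.200 + 0.001 = 0.201.

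| Share who know their mesh (assumed) | Shift 0.05 SD | Shift 0.10 SD |
|---|---|---|
| All | 9% | 20% |
| Half | 6% | 9% |
| One quarter | 5% | 6% |

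With an assumed 20% loss (n = 200, all aware), the threshold is 1.96 × √(2/200) = 0.196 SD and the two rates are about 8% and 17%.

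The gain from masking is the step between the row that would apply under the current plan and the row that would apply with masking. The documents fix neither row. If nearly every patient would otherwise learn the mesh, the gain for a 0.10 SD shift could be from 20% to 6%. If only a quarter would learn it anyway, the rate is already about 6% and little is gained.

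**The case against.** Open-label is a declared choice, and nothing else in the documents contradicts it. The application form asks for a summary, which need not argue every design choice, and the consent form was not in the text reviewed. Patients may never be told their mesh. Even if they are, both products are lightweight polypropylene meshes in interchangeable use with good results, and the text gives patients no ground to expect one to feel better. The larger false-positive figures need every patient to be aware and a consistent shift in one direction, which the documents give no reason to expect. All of this stands, and it limits the claim to a design improvement of unknown benefit.

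Three objections to the remedy also have force:

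- **Who collects follow-up.** A reader might infer from Part II, section F, where the 6-month and 1-year visits are called non-routine, that the study is free to choose a masked collector. That passage is about billing and does not show who can make the contacts.
- **The coordinator.** This person reports negative trends and adverse events to the IRB (Part IV, item 3), and patients are tracked in EPIC with the surgery admission attached. The coordinator may therefore be hard to mask.
- **Consent and cost.** Withholding the identity of an implanted device for a year has to be agreed at consent. The documents give no cost or workload figures, so calling the change cheap is a judgment.

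These points make collector masking secondary. They do not defeat the main step, which is not telling the patient.

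**Conclusion.** The point holds as a low-cost improvement centered on the patient. A patient-rated effectiveness measure that asks about sensation of the mesh is collected in a trial declared open-label, with no reason visible and with circumstances that appear to suit patient masking.

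Two stronger readings are tempting, and the documents support neither. One is that the trial's pain and comfort comparison has a false-positive rate of 9% or 20%. Those figures are hypothetical: only the 500 and the 0.05 come from the plan, while the shift, its common direction, full awareness, equal arms and the test are assumed. The other is that patients will be told their mesh and that results will be biased as a consequence. The text does not say what patients are told, and any shift may be small.

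Masking would reduce the risk for patient-rated outcomes and would not remove it. It would also not settle whether recurrence reported by telephone is accurate, which is a separate measurement question.

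**What to change.** In Part IV, item 2, replace open-label with patient-masked and add the following:

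1. The mesh is not disclosed to the patient until the 1-year assessment is complete, unless it is needed for care or the patient asks. Any disclosure is recorded with its date.
2. The baseline CCS and VAS are completed before the envelope is opened.
3. CCS and VAS forms are keyed by study ID and do not show the mesh. Study-ID linkage is already planned for the NASA-TLX forms, and Part II, section C already provides for a separate master list.
4. Where existing staff allow, follow-up ratings are collected by a team member who has not looked up the operative record.

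If open-label is kept, state why, and say whether patients are told their mesh.

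**Cost.** Protocol and consent wording, an unmasking route and some staff time, which the documents do not let one quantify. No extra patients, visits or procedures are needed, and the choice of mesh in the operating room is unaffected.

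**Limits.** Masking will leak through the medical record, the recorded lot number and contact with the surgical team. The attending and residents stay unmasked. Length of stay, complications, operative timing, NASA-TLX and recurrence examined by the attending are not protected.

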This section is not applicable to my study

1. Where will the devices be stored?	Explain. Devices are stored in the Operation Room (OR) and are in stock in the OR holding room at New Hanover Regional Medical Center.
2. Who will receive and manage inventory for the devices throughout the study?	Name: OR Staff Title: Nurses and Doctors
3. Who will have access to the devices?	Name: OR Staff Title: Nurses and Doctors
4. How will the devices be accounted for?	Explain. Devices that are available on stock at the hospital will be used and the Lot number will be recorded.

5. What protections are in place to prevent loss or improper use?	Explain. These are devices are currently FDA approved and used on a daily basis at NHRMC so there are already precautions in place to protect them.
---	---

Part II: Study Subjects and Procedures

Complete the sections that apply to your study.

A. Subject Enrollment and Demographics:

This is a listing of the **target** study population. Check all that may apply.

You don't have to meet the anticipated subject enrollment number, but you can't exceed it without an amendment to increase the number anticipated at this site.

 Healthy Volunteers	 Chronically Ill	 Placebo (non active medicine)
 Employees	 Mentally Ill	 No Treatment Condition (control group is involved that receives no study-related treatment)
 Students	 Terminally Ill	 Storage of Specimens for Future Use
 Hospitalized Patients	 Use of Banked Specimens	 Multi-center Study: Subject Enrollment
 Male	 Use of Fetus/Fetal Tissue	# anticipated this site
 Female	 * Indigent/Uninsured	 Single Site Study: Subject Enrollment
 Adults	 * Non-English Speaking	# anticipated this site 511
 Children (under 18) (complete section V)	 * Limited or No Literacy	
 * Pregnant (see below)		

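### Envelope opening is fixed only to the day of surgery, so the mesh may be known before the baseline scales, the timed pre-mesh steps and the resident's assignment

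*Combined protocol and SAP*

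**What the plan says.** All of this is in Part IV, item 2 (study design, methods and procedures), except where noted.

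- **Time of allocation:** "On the day of surgery, patients agreeing to participate in the study will be randomized to receive either one of two meshes". No operative step or precondition is attached.
- **Mechanism:** an electronic random number generator produces the sequence, and "the random assignments will be placed inside opaque, sequential envelopes". The plan adds: "The envelopes will be opened, in order, which will guarantee a random assignment of subjects to each study arm". It does not say who holds or opens the envelopes, or whether a log ties each one to a patient.
- **Baseline scales:** "Prior to the surgery, patients will be given the Carolinas Comfort Scale (CCS) and Visual Analog Scale (VAS"). Their order relative to the envelope is not given.
- **Blinding and operator:** "This will be a prospective open-label randomized study". One attending performs all cases with his standard technique.
- **Findings at operation:** bilateral hernias may be "either found preoperatively or intra-operatively"; they count as one hernia and get the same mesh on both sides.
- **Resident data:** PGY level, the share of the case taken by the resident (a percentage the attending determines) and the times for the critical portions are documented. Those portions include access and takedown, which come before mesh placement.
- **Analysis:** outcomes and resident performance are compared by resident level and mesh type, at p<0.05. No change score, baseline adjustment or covariate is named.
- **Supply (section D, Research Involving Devices):** "Devices are stored in the Operation Room (OR) and are in stock in the OR holding room".

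**The concern.** A baseline rating, the time taken before any mesh is handled, and the choice of resident should all be unaffected by allocation. The plan does not secure this, because the envelope may be opened at any time that day.

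The secondary goal is the most exposed. If the attending knows the mesh when choosing the resident or dividing the case, resident level and share become post-randomization variables, and a mesh comparison by level is no longer protected by randomization. If access and takedown are timed with the mesh known, total operative time can carry a performance effect from steps that the mesh cannot physically influence.

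Two lesser matters follow. A patient who knows the mesh may rate baseline pain or comfort differently, which would matter in any analysis that uses the baseline. And if the envelope is opened before the operative findings are settled, some randomized patients may receive neither mesh; the plan does not say how they would be analyzed.

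**Working it through.** The plan gives no figure to reproduce: the approximately 500 subjects come with no effect size, SD, power or dropout rate. The check is therefore a comparison of the text, followed by two illustrations on stated assumptions.

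**1. What must precede allocation, and whether the plan says it does**

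| Item | Timing in the plan | Order relative to opening |
|---|---|---|
| Baseline CCS and VAS | before surgery | not stated |
| Resident level and role | documented; time not given | not stated |
| Access and takedown | timed; precede mesh placement | not stated |
| Side(s) to be repaired | before or during surgery | not stated |

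The form asks applicants to "describe the study in sequential order as it is to be conducted at this institution", and randomization is written before the scales. That is weak evidence: the same narrative puts demographics and medical history after randomization, and the approach to residents, which precedes the study, after the one-year follow-up. The sound conclusion is that the order is open.

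**2. If a baseline-using analysis were added**

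Assumptions: n = 250 per arm (equal split of 500), two-sided 0.05, no true mesh effect, outcome SD 1, baseline–outcome correlation r of 0.3 to 0.7, baseline shifted by b SD in one arm.

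- Change score: m = b / [√(2(1−r)) · √(2/n)].
- ANCOVA: m = r·b / [√(1−r²) · √(2/n)].
- False-positive rate = 1 − Φ(1.96 − m) + Φ(−1.96 − m).

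Example, change score with r = 0.5, b = 0.10: √(2/250) = 0.0894, m = 0.10/0.0894 = 1.118, rate = 20.1%.

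| Shift b | Change score | ANCOVA |
|---|---|---|
| 0.05 SD | 8–11% | 5–9% |
| 0.10 SD | 16–30% | 6–20% |
| 0.20 SD | 47–82% | 11–59% |

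A comparison of follow-up scores alone does not use the baseline, so its rate stays at 5%.

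**3. If some patients receive neither mesh**

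Assumptions: true difference d = 0.25 SD, 500 enrolled, two-sided 0.05, a fraction f in each arm receiving neither mesh. Power ≈ Φ(d√(n/2) − 1.96). With f = 0: 0.25 × √125 = 2.795, power 79.8%.

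- Early opening: everyone is randomized and analyzed, so the effect is diluted to d(1−f) with n = 250.
- Late opening: non-recipients are not randomized, so d is intact but n = 250(1−f).

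| f | Early opening | Late opening |
|---|---|---|
| 2% | 0.245 × √125 = 2.739 → 78.2% | 0.25 × √122.5 = 2.767 → 79.0% |
| 10% | 0.225 × √125 = 2.516 → 71.1% | 0.25 × √112.5 = 2.652 → 75.5% |

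The gain from late opening is 0.8 points at 2% and about 4.5 points at 10%.

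**The case against.** The other side has a good deal to say, and much of it stands.

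- **Concealment.** A reader might infer that assignments are predictable. The documents do not support this: a generated sequence in opaque, sequential envelopes, opened after written consent, conceals allocation at enrolment. What remains is narrower. The plan's claim of a guarantee is too strong when no envelope is tied to a patient before opening. That matters most if several patients share a day's list, which the plan does not mention.
- **Hernia confirmation.** A reader might infer that the envelope is opened before the hernia is confirmed. No sentence says so; an unfixed time could equally fall after confirmation. Only possibly before is supported.
- **Baseline scores.** A reader might infer that the score comparisons are biased. The plan names no analysis that uses the baseline, and does not say that patients learn their mesh before rating.
- **Resident share.** The percentage determined by the attending appears in a list of items to be documented, and may be an estimate made after the case. It cannot be read as a decision taken beforehand. The assignment of a resident of a given level remains unprotected either way.
- **Motive.** The two meshes are used interchangeably at the site and one attending uses his standard technique, so no reason for differential behavior is shown. This lowers the likelihood but does not remove the opportunity.
- **Power.** A reader might set 71.1% against 79.8% and credit late opening with the whole difference. That is wrong, because late opening also loses the non-recipients.
- **Choice of time.** Opening after the scales but before incision would settle the baseline point alone. It would leave access and takedown exposed.

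**Conclusion.** The point holds as a gap in timing and procedure. As written, the plan permits the mesh to be known before the baseline scales, the pre-mesh operative steps and the resident's assignment, and possibly before the side or sides to be repaired are settled. It does not show that this will happen.

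The consequence falls mainly on the resident comparisons of time and ease of use. For patient-reported scores it is conditional on a change-score or baseline-adjusted analysis: at an assumed shift of 0.05 SD, the false-positive rate would be 8–11% for a change score and 5–9% for ANCOVA. The effect on power is modest, 0.8 to 4.5 points, and depends on an assumed d of 0.25, equal arms and an assumed 2–10% receiving neither mesh, none of which the documents give. No figure in the plan changes. It is worth correcting before enrolment because the remedy is cheap.

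**What to change.** State the following in Part IV, item 2:

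1. The CCS and VAS are completed, and the resident's level and planned role recorded, before any envelope is opened.
2. A named role (for example, the study coordinator) holds the sealed, numbered envelopes, writes the patient's study ID and the date on the next one before it is opened, and keeps a log.
3. The envelope is opened in the operating room after takedown, once the side or sides to be repaired are recorded, immediately before mesh placement.
4. How patients randomized but not given a study mesh are analyzed.

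The cost is a change of wording, a log, a brief pause in the case, and both meshes within reach; they are already stocked in the operating room. The change protects only what comes before opening. Mesh placement, closure, the NASA-TLX and the follow-up ratings stay unblinded, so some performance effect on operative time can remain.
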